6.2.2 Study Drug Discontinuation

If study drug administration is discontinued, the reason for discontinuation will be recorded.

6.3 Details of Procedures

6.3.1 Study Materials

Bristol-Myers Squibb (BMS) will provide ipilimumab at no cost for this study.

6.3.2 Safety Assessments

All patients who receive at least one dose of ipilimumab will be considered evaluable for safety parameters. Additionally, any occurrence of a SAE from time of consent forward, up to and including follow-up visits will be reported. See Section 8: Adverse Event Reporting.

Safety will be evaluated for all treated patients using the National Cancer Institute (NCI) Common Terminology Criteria for Adverse Events (CTCAE), Version 4.0 (http://ctep.cancer.gov). Safety assessments will be based on medical review of adverse event reports and the results of vital sign measurements, physical examinations, and clinical laboratory tests.

6.4 Criteria for Evaluation

6.4.1 Safety Evaluation

Refer to the NCI CTCAE, Version 4.0 (http://ctep.cancer.gov). SAEs will be assessed every three weeks during the first four cycles of ipilimumab and every 12 weeks during the fifth through eighth cycle of ipilimumab.

6.4.2 Efficacy Evaluation

The **primary endpoint** is fraction of patients who achieve an undetectable PSA (≤ 0.2 ng/ml). Pursuant to that endpoint, we will check the PSA every 3 weeks during the first 4 cycles and every 6 weeks during weeks 12-24, then every three months as the patient is being followed (planned follow up through year 5).

The **secondary endpoints** explore the objective responses achieved in the realm of non-progression of disease and tumor regression, as well as provide an opportunity to learn more about the immune response itself. Part of this assessment is PSA-based and part is based on radiographs (bone scans and CT scans). We will use the procedures described for the primary endpoint, above, to look at response endpoints. Additionally, a CT scan of the chest/abdomen/pelvis and bone scan at baseline, week 12, week 24 and every 6 months thereafter will be done for comparison. We will also perform a history and physical prior each cycle to detect new pain that could indicate cancer progression. After the 8 cycles of ipilimumab, patients will have their PSA checked every 3 months, either at the study center or by an outside provider. Their survival status will be assessed by telephone survey every 6 months for a maximum of 5 years. For the correlative work, we will collect blood samples prior to each infusion of ipilimumab and quantify the immune response. Once the study is complete, we will compare the objective response with the depth of the immune response.

6.4.2.1 Definitions of PSA-Related Secondary Endpoints

PSA progression: PSA increase of \geq 25% and at least 2 ng/mL from baseline or nadir PSA achieved, confirmed by a second measurement at least three weeks later.

PSA nadir: Lowest PSA reached that was confirmed by a second equal or lower measurement.

PSA response: As recommended by the PCWG2 definitions. We will not apply a strict definition for PSA response. The primary endpoint is the proportion of patients with a PSA < 0.2 ng/ml on this study. Waterfall plots will be used to describe PSA changes while on study.

Maximum percentage of PSA reduction in each patient. Percentage of PSA reduction will be defined as [1 - (lowest PSA attained on study)/(PSA at study entry)] x 100. This formula only applies to PSAs that have decreased, and not those that have remained constant, i.e. the same as the baseline measurement.

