3.5 End of Treatment Cycles

Patients who progress radiographically on ipilimumab after completion of the initial four doses will not receive more immunotherapy once progression has been documented. For soft-tissue lesions, the RECIST criteria for progression (see 6.4.2) will be used. For bone lesions, there should be ≥ 2 new lesions confirmed on a second scan at least 4 weeks later. Progression will not be assessed until completion of the initial 4 cycles of treatment in order to avoid premature discontinuation of therapy.

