6 STUDY PROCEDURES AND OBSERVATIONS

6.1 Time and Events Schedule for Protocol CA184059

		Induction* (Cycles 1-4)			Between Treatments			Maintenance* (Cycles 5-8)			Every 6 Month Follow Up*		
T //P 1	Scree . #	Wk	Wk	Wk	Wk	Wk	Wk	Wk	11/1 24	WI 26	XX/1 40	W/I (0	Evel Fc
Test / Procedure	ning#	1	4	/	10	12	18	23/24	Wk 24	Wk 36	Wk 48	Wk 60	Π
Informed Consent	X												
Inclusion / Exclusion Criteria	X												
Demographics, medical history, concurrent medical conditions	X												
Testosterone level	X												
Serum samples for hepatitis panel and HIV, if high index of suspicion	X												
ECOG performance status	X	X	X	X	X	X	X	X	X	X	X	X	
Blood collection for correlative studies ¹		X	X	X	X								
Physical Exam	X	X	X	X	X	X	X	X	X	X	X	X	
Vital Signs	X	X	X	X	X	X	X	X	X	X	X	X	
Weight		X	X	X	X				X	X	X	X	
Bone Scan ²	X					X		X		X	X	X	
Chest, Abdomen & Pelvis CT ²	X					X		X		X	X	X	

CBC with differential	X	X	X	X	X	X	X	X	X	X	X	X	
Chemistry Panel: Creatinine, BUN, electrolytes (sodium, potassium, chloride), glucose, bilirubin alkaline phosphatase, ALT, AST, calcium, ³	X	X	X	X	X	X	X	Х	Х	X	Х	X	
LDH	X												
Autoimmune Profile: TSH, free T4	X	X	X	X	X				X	X	X	X	
PSA ⁴	X	X	X	X	X	X	X	X	X	X	X	X	
Concurrent medications (include documentation of androgen suppression therapy)	X	X	X	X	X				X	X	X	X	
Adverse Effects Recorded	X	X	X	X	X		_		X	X	X	X	
Ipilimumab		X	X	X	X				X	X	X	X	
Telephone Contact													X

^{*} Cycle 1-8 procedures can be done +/- 3 days and Long Term Follow-Up can be done +/- 2 weeks.

#Screening procedures must be done within 28 days of first treatment

^{**}PSA, Autoimmune profile, LDH, CBC Diff, Chem panel including Creatinine, BUN, electrolytes (sodium, potassium, chloride), glucose, bilirubin, alkaline phosphatase, ALT, AST, calcium, phosphorus and Correlative **baseline samples** DO NOT need to be repeated on Cycle 1 Day 1 if done within 7 Days of Cycle 1 Day 1

¹ Per outlined correlative studies

² Imaging Studies will also be done every three months until radiographic progression

³ Available labs (i.e. chemistries and blood counts) will be reviewed prior to each infusion

⁴ PSA will be done until radiographic progression

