6.4.4 Response Endpoints

Ipilimumab is expected to trigger immune-mediated responses, which require activation of the immune system prior to the observation of clinical responses. Such immune activation may take weeks to months to be evident. Some patients may have objective increase of tumor lesions or other disease parameters (based on study indication, i.e., hematologic malignancies) within 12 weeks following start of ipilimumab dosing. Such patients may not have had sufficient time to develop the required immune activation or, in some patients, apparent mRECIST progression may represent infiltration of lymphocytes into the original tumor or blood. In conventional studies, such apparent radiographic progression or relevant laboratory parameter increases during the first 12 weeks of the study would constitute PD and lead to discontinuation of imaging to detect response, thus disregarding the potential for subsequent immune-mediated clinical response. In this study, it may not represent actual tumor progression.

Therefore, patients with tumor progression detected or lack of laboratory parameter response documentation prior to week 12 but without rapid clinical deterioration should continue to be treated with ipilimumab and clinically observed with a stringent imaging schedule to allow detection of a subsequent tumor response. This will improve the overall assessment of the clinical activity or ipilimumab and more likely capture its true potential to induce clinical responses. Investigational Product: IPILIMUMAB

The investigational product is defined as a pharmaceutical form of an active ingredient being tested as a reference in the study, whether blinded or unblinded. In this study, the investigational product is ipilimumab.

Other medications used in the study as support or escape medication for preventative, diagnostic, or therapeutic reasons, as components of the standard of care for a given diagnosis, are considered non-investigational products. In this protocol, there are no non-investigational product(s).

Identification

Ipilimumab is available in 5 mg/mL single-use vials (10 mL or 40 mL). The sterile solution in the vial is clear and colorless. Ipilimumab is administered via intravenous infusion only.

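### The PSA progression definition sets no earliest assessment time, so a confirmed rise during the first 12 weeks counts as an event, which fits poorly with sections 6.4.4 and 3.5

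*Combined protocol and SAP*

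**What the plan says.** - **Definition (6.4.2.1).** PSA progression is a rise of 25% or more and "at least 2 ng/mL from baseline or nadir PSA achieved, confirmed by a second measurement at least three weeks later". No starting week is given. The nadir must itself be confirmed by a second equal or lower value.
- **Schedule (6.4.2 and 6.1).** The plan says "we will check the PSA every 3 weeks during the first 4 cycles and every 6 weeks during weeks 12-24". The time and events table places PSA at weeks 1, 4, 7, 10, 12, 18, 23/24, 24, 36, 48 and 60, and notes that "Cycle 1-8 procedures can be done +/- 3 days".
- **Early changes (6.4.4).** In conventional studies "such apparent radiographic progression or relevant laboratory parameter increases during the first 12 weeks of the study would constitute PD". The section then adds: "In this study, it may not represent actual tumor progression". PSA is not named.
- **Deferral (3.5).** "Progression will not be assessed until completion of the initial 4 cycles of treatment in order to avoid premature discontinuation of therapy". The surrounding text covers soft-tissue and bone lesions and the ending of immunotherapy. The 12-week rule in 5.1.4 is expressly radiographic.
- **Analysis (8.5).** Time to PSA progression and time to progression by any measure are estimated by Kaplan-Meier, and time to PSA progression is the example given for the Cox models. There is no rule for early rises, and none saying whether the event is dated at the first rise or at its confirmation.
- **Primary endpoint (2.1, 8.3).** PSA of 0.2 ng/ml or less after starting ipilimumab, with success judged at 6 months. Neither section excludes a man who had an earlier PSA rise.

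**The concern.** Section 6.4.4 argues that a benefit from this drug may follow an initial worsening, and that changes in the first 12 weeks should be read with that in mind. The PSA progression endpoint makes no such allowance. A man whose PSA climbs over the first two or three doses and later becomes undetectable would be a success on the primary endpoint and an early failure on time to PSA progression.

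Two secondary objectives are exposed: time to PSA progression, and time to progression by any measure if that composite includes PSA, which the plan does not define. Section 2.2 also relates IRAEs both to complete PSA response and to time to progression. The same man would then count in opposite directions in the two analyses. Any distortion runs against ipilimumab and is greatest in delayed responders. If the rule is not settled in advance, the choice can be made after the PSA courses have been seen.

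**Working it through.** The plan states no figure for early PSA rises, so there is none to reproduce on this point. The only calculable design figures are the two-stage sample size and its error rates, and PSA progression does not enter them.

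**1. When can an event arise?** The inputs are the nominal PSA weeks from 6.1 and the three-week minimum gap from 6.4.2.1. For each first rise, take the earliest later visit at least 21 days away:

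- First rise at week 4: confirmed at week 7 (21 days).
- First rise at week 7: confirmed at week 10 (21 days).
- First rise at week 10: week 12 is only 14 days later, so confirmed at week 18.
- First rise at week 12: confirmed at week 18 (42 days).

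Rises first seen at weeks 4 and 7 can therefore be both seen and confirmed before week 12. The earliest declaration is week 7. Week 4 is the event date only under back-dating.

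**2. Effect of the visit window.** With 3 days either way at both visits, the gap between weeks 4 and 7 runs from 21 − 6 = 15 to 21 + 6 = 27 days. If it is under 21 days, confirmation of a week 4 rise moves to week 10, still before week 12.

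**3. Threshold.** The PSA required is the larger of 1.25 × baseline and baseline + 2. The two are equal at a baseline of 8 ng/mL (1.25 × 8 = 8 + 2 = 10). Below 8 the absolute floor governs: a man at 0.5 must reach 2.5, and a man at 4 must reach 6. Men with low entry PSA trigger the rule less easily.

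**4. An invented illustration.** Take PSA 10 at baseline, 12.6 at week 4, 13 at week 7, 4 at week 12 and 0.2 at week 24. At week 4 the rise is 2.6 ng/mL, or 2.6/10 = 26%, so both criteria are met, and week 7 confirms it. The same man meets the primary endpoint at week 24. The definitions allow this course; the documents do not report one.

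**5. Size per man.** With all 30 men at risk and no earlier censoring, each early event lowers the Kaplan-Meier estimate by 1/30 = 3.3 points. The number of such men is not given. As an assumed range only, 1 to 6 men would give 3.3 to 6/30 = 20.0 points. If exactly 6 men met the primary endpoint, 1 to 6 overlaps would be 1/6 = 17% to 100% of the successes.

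**6. Effect of a week 12 start.** The earliest event date moves from week 4 to week 12 (8 weeks). The earliest confirmation moves from week 7 to week 18 (11 weeks).

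**The case against.** The strongest reply is that the plan already contains deferral wording and that 6.4.4 is being asked to carry too much.

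- The sentence in 3.5 has no modality qualifier, so it could be read as covering PSA. That is possible, but everything around it is radiographic and about stopping treatment. If it does cover PSA, it conflicts with 6.4.2.1. Either way the two need reconciling.
- A reader might infer that the protocol itself declares the PSA rule unsuitable for this drug. It does not. Section 6.4.4 never names PSA, its example of other disease parameters is haematologic malignancy, and it says only that early change may not be progression. Its stated consequence is continued treatment and imaging, which the plan delivers, since only radiographic progression ends therapy under 3.5 and 5.1.4. PSA is nevertheless the trial's main laboratory measure of disease, so the text needs clarifying.
- The synopsis refers to PCWG2 criteria. Whether that source handles early rises cannot be judged from the documents, and 6.4.2.1 writes out its own definition without such a rule.
- Success on a PSA-level endpoint and an event on a time-to-event endpoint are different quantities and can properly coexist. This stands: the overlap is not a logical contradiction. What remains is that the early event is counted under a reading that 6.4.4 puts in doubt.
- A reader might size the problem from the 9.7% in section 1.4, giving 30 × 0.097 = 2.9 men. That figure is for pretreated melanoma patients and concerns disease control after lesion growth or new lesions, not PSA. Applied instead to the 3 to 9 successes implied by 10% to 30% of 30, it would give 0.3 to 0.9 men. The documents support neither calculation.

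**Conclusion.** The point holds as a gap in the definition of a secondary endpoint. As written, a rise seen at week 4 and confirmed at week 7, or at week 10 if the visit window shortens the gap, is PSA progression. Sections 6.4.2.1, 6.4.4 and 3.5 do not agree on whether it should be.

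A reader might infer that progression can be declared at week 4. The confirmation requirement rules that out, and week 4 is at most a back-dated event date that the plan neither adopts nor excludes. A reader might also infer that the trial's main conclusion is at risk. It is not: the primary test, the sample size, the type I error and the power do not depend on PSA progression.

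The effect is about 3.3 Kaplan-Meier points per affected man before week 12, assuming 30 men at risk and no earlier censoring. How many men would be affected is unknown. The effect reaches the Cox models for time to PSA progression, and reaches progression by any measure only if that composite includes PSA. The inconsistency is worth resolving before analysis because doing so is cheap and otherwise leaves a choice open to hindsight.

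**What to change.** Reconcile 3.5, 6.4.2.1 and 6.4.4 by adding to 6.4.2.1, for endpoint scoring only and with no bearing on treatment:

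*PSA rises before week 12 are recorded but do not count as PSA progression. Progression is first assessable at the week 12 PSA, against baseline or the confirmed nadir as defined in this section, confirmed at least 3 weeks later, and dated at the first qualifying PSA at or after week 12.*

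State whether progression by any measure includes PSA and, if so, apply the same rule to that component. Report the unrestricted definition as a sensitivity analysis. In it, count as events the men with a confirmed early rise who start other cancer therapy before week 12.

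**Cost.** A short addition to the text and one extra analysis run, with no new visits. Men who truly progress early are dated up to about 8 weeks later, and their earliest confirmation moves by about 11 weeks. Men who start other therapy before week 12 would be censored in the main analysis under 8.5 rather than counted, which could favour ipilimumab. The sensitivity analysis shows both effects.

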interacting with the CTLA-4 receptor on the T cells. This interaction downregulates the immune response, thus allowing cancer cells to escape detection.³ Immunotherapy with anti-CTLA antibody (ipilimumab) shows promise in Phase I studies of men with CRPC who have progressed through current therapeutic options.⁴ At our institution, twenty-six metastatic prostate cancer patients have started this therapy. Of thirteen evaluable patients, four have had confirmed PSA responses (PSA decrease of 50% or greater from reference value confirmed by a second measurement at least 3 weeks later), including one with objective radiologic as well as PSA complete response, ongoing for over 2 years as of September 2009. Notably, these patients responded despite having considerably more extensive and more heavily pre-treated disease than the population targeted in this proposal.

[figure not shown]
We are collaborating with [name], an oncologist with an interest in prostate cancer immunology at USCF. All correlative studies will be done in [name] laboratory. The total amount of blood required for these studies is 60 ml just prior to the first four ipilimumab doses (weeks 1, 4, 7, 10). We will perform correlative studies examining the ratio of T effector to T regulatory cells before and after treatment with ipilimumab.[name] lab has identified its own set of prostate cancer antigens. The names of these antigens are not specifically outlined because they are proprietary at this time. The results of all studies will be correlated with outcomes and side effects in exploratory analyses.

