 - Serum PSA will be drawn every 6 weeks for weeks 12-24, then every 12 weeks.
 - Complete blood count with automatic differential, comprehensive chemistry panel and Autoimmune Panel (TSH, free T4) will be obtained prior to administration of each dose of ipilimumab, which will be given to eligible patients every 12 weeks beginning at week 24.

- Available lab results (i.e. chemistries and blood counts) will be reviewed prior to administration of ipilimumab.
- o Imaging and Diagnostic: A radionuclide bone scan and CT scan (chest, abdomen and pelvis) will be obtained at baseline, week 12, week 24, and every three months thereafter until radiographic progression. Scans may be obtained sooner for concerning symptoms.

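### The PSA nadir rule in Section 6.4.2.1 can never return a lowest PSA seen once and followed by a rise, so PSA progression can be dated late; separately, the maximum-reduction formula gives no value to patients whose PSA did not fall

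*Combined protocol and SAP*

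**What the plan says.** Section 6.4.2.1 gives the PSA definitions for the secondary endpoints.

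- Nadir: "Lowest PSA reached that was confirmed by a second equal or lower measurement".
- Progression: a rise of 25% or more and "at least 2 ng/mL from baseline or nadir PSA achieved, confirmed by a second measurement at least three weeks later". The text does not say when baseline applies and when the nadir does.
- Maximum percentage reduction: one minus the ratio of the "lowest PSA attained on study" to the PSA at entry, times 100. No confirmation is required. The text adds: "This formula only applies to PSAs that have decreased, and not those that have remained constant".
- Display: "Waterfall plots will be used to describe PSA changes while on study". This sentence stands under PSA response, apart from the reduction formula.

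The Synopsis, Section 2.2 and Section 6.4.2.1 all set maximum reduction as an endpoint for every patient. Section 8.5 plans a Kaplan-Meier estimate of time to PSA progression and names that endpoint as its example for Cox regression. It plans no numerical summary of maximum reduction. Section 8.4 assigns secondary endpoints to the ITT population where possible, for patients in whom the endpoint is measured.

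PSA is drawn every 3 weeks in cycles 1 to 4. After that, Section 3.3.2 says: "Serum PSA will be drawn every 6 weeks for weeks 12-24, then every 12 weeks". Note 4 to the schedule in Section 6.1 sets the end of testing: "PSA will be done until radiographic progression".

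**The concern.** The nadir rule asks for confirmation in a direction that a rising PSA cannot supply. A patient who reaches a minimum once and then rises is a typical candidate for PSA progression, and in that patient the true minimum is rejected. The reference is then too high relative to the lowest PSA recorded, the threshold for progression is higher, and the date can slip by one or more visits. From week 12 each visit of slippage costs 6 to 12 weeks.

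The section is also at odds with itself. It measures depth of decline from the lowest PSA recorded and progression from a different, confirmed low.

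The reduction formula raises a separate point. A patient with a flat or rising PSA has no value, so the endpoint is undefined for part of the group for which it was set. If someone later summarised it over the patients who have a value, the result would look more favourable than one over all patients.

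**Working it through.** **Direction of the effect.** Let ref be the reference PSA. Progression requires PSA at or above max(1.25 × ref, ref + 2), with the same level met at the next PSA at least 3 weeks later. The threshold increases with ref. The written nadir, or baseline where no nadir exists, is never below the lowest observed PSA. Any rise that meets the written rule therefore also meets the lowest-observed rule at that visit or earlier, so the written rule gives the same date or a later one. As a check, in 100,000 random series without ties the written rule returned the minimum 0 times. A repeated minimum is unaffected.

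**Worked series.** Weeks are 1, 4, 7, 10, 12, 18, 24, 36, 48, 60, as far as each series runs. These are constructed examples.

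| PSA (ng/mL) | Lowest observed: ref, threshold, date | Written nadir: ref, threshold, date |
|---|---|---|
| 8, 4, 2, 1, 3.2, 5, 8 | 1, max(1.25, 3) = 3, week 12 | 2, max(2.5, 4) = 4, week 18 |
| 12, 8, 5, 1.5, 3.6, 5, 6.5, 9, 12 | 1.5, max(1.875, 3.5) = 3.5, week 12 | 5, max(6.25, 7) = 7, week 36 |
| 10, 9, 8, 7, 6, 3, 5.5, 6.5, 8.5, 11 | 3, max(3.75, 5) = 5, week 24 | 6, max(7.5, 8) = 8, week 48 |
| 10, 4, 6.5, 7, 8, 9, 11, 12.8, 15 | 4, max(5, 6) = 6, week 7 | 10, max(12.5, 12) = 12.5, week 36 |
| 8, 4, 2, 1, 5, 9, 14 | 1, 3, week 12 | 2, 4, week 12 |

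The last row shows that a steep rise passes both thresholds at once. In the first row the nadir is 2, but the reduction formula uses 1: 1 − 1/8 = 87.5%, against 1 − 2/8 = 75% from the nadir.

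**How often, in 30 patients.** This needs a simulation.

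- Inputs from the documents: the PSA schedule, and a median entry PSA of 4 ng/mL. In the Section 1.2 table, 360 of 360 + 383 = 743 men above 0.2 (48%) were at or below 4.
- Assumed: 15 to 35% of patients fall then rise; log SD 0.8; halving/doubling times of 4/12 or 6/18 weeks; turning point between weeks 4 and 24; 10% noise; visits to week 108.
- Plausibility: these inputs give a decline of at least 50% in 12 to 33% of patients. The documents show 2/14 (14%) and 10/45 (22%) in Section 1.3.6, and in Section 1.2 "Of thirteen evaluable patients, four have had confirmed PSA responses" (31%).

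| Setting | Dated later | Of 30 | Median moved |
|---|---|---|---|
| 15 to 35% fall then rise | 3.8 to 13.0% | about 1 to 4 | 4 of 30 runs, by one visit |
| 25% fall then rise | 5.7 to 10.8% | 2 to 3 | 0 of 6 runs |
| Median entry PSA 3 or 5 | 4.1 to 14.6% | about 1 to 4 | 3 of 24 runs |
| PSA testing stops early (assumed median 26 or 52 weeks) | 2.1 to 7.6% | about 1 to 2 | 2 of 20 runs |

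Of the delayed patients, 8 to 24% slip two or more visits. Larger effects need stronger assumptions. With every patient falling then rising from a median entry PSA of 8, about 30 to 34% of those progressing under both rules are dated later.

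**Spurious lows.** If 2 to 5% of readings were wrongly halved (assumption), progression would be brought forward in 1.5 to 6.4% of patients under the lowest-observed rule, against 0.3 to 0.8% under the written rule. With 5% halved, and the two kinetics in turn, total misdating early or late is 42% and 48% under the lowest-observed rule, against 45% and 50% as written. A repeat gave 44.7% and 49.7% against 46.4% and 50.5%. The totals are about the same.

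**Maximum reduction.** No size can be derived from the documents. For illustration, suppose the falls among decliners are spread evenly from 5% to 95%. Their median is 50%. Over all 30 patients, with non-decliners counted as 0, it is 45%, 38%, 26% or 2.5% if 3, 6, 10 or 15 patients do not decline.

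**The case against.** The best defence of the nadir rule is that confirmation guards against a single spurious low. That is a legitimate aim, and the spurious-low figures show that the rule does reduce early dating. A reader might infer that the lowest-observed rule is more accurate, or that the written rule errs mainly late. The results do not support either: total misdating is about equal, and any early/late split takes the lowest-PSA date as the truth, which favours that rule by construction. The case for change is the logic of the definition and its conflict with the reduction formula.

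Section 6.4.4 warns that laboratory rises in the first 12 weeks may not be true progression, and Section 3.5 defers assessment of progression until four cycles are complete. The lowest-observed rule can bring dates into that window (week 7 in the fourth series). This stands as a consequence of the change. It does not affect treatment, because Sections 3.5 and 5.1.4 tie discontinuation for progression to radiographic findings.

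On the reduction formula, a reader might infer that the plan will overstate activity. The documents do not support that. Section 8.5 plans no summary restricted to decliners, and nothing ties the waterfall plot to the formula, so it may already show everyone. Nor is the population unaddressed: Section 8.4 names ITT. But that rule covers patients whose endpoint is measured, so it does not supply a value for patients to whom the formula gives none.

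The size is small, the patients behind the response rates used for plausibility had more advanced disease, and there is no comparator arm for a delay to favour. All of that stands.

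**Conclusion.** Both points hold on the wording, and no other section repairs them. The nadir rule excludes every minimum seen once and followed by a rise, can only leave the date unchanged or move it later, and leaves two different lowest PSAs in use for one patient. The reduction formula leaves patients without a fall with no value for an endpoint set for everyone.

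Confidence in the wording logic is high. The numbers depend on the assumed PSA kinetics and on the share of patients who fall then rise: about 1 to 4 of 30 dated later, or about 1 to 2 if testing stops early, which is closer to the schedule's own stopping point. The Kaplan-Meier median is usually unchanged.

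A reader might infer that the planned Cox associations are biased, or that the trial's main conclusion is at risk. Neither follows. No bias in the Cox associations has been shown, and the primary endpoint, the two-stage design in Section 8.3 and the radiographic discontinuation rules do not use these definitions. This is a correction that should be made before analysis, so that neither the reference value nor the denominator is chosen after results are seen.

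**What to change.** In Section 6.4.2.1:

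- Define the nadir at each visit as the lowest PSA observed up to that visit, including baseline, and make it the reference for progression.
- Keep the confirmation of the rise at least three weeks later.
- Report time to PSA progression under the confirmed-nadir definition as a sensitivity analysis.
- Apply the percentage-change formula to every patient with a post-baseline PSA, allowing zero or negative values, and state that the waterfall plot and any numerical summary include all of them.

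The cost is a few sentences, using PSA data already collected, with no change to visits, treatment or sample size. The downside is that one spurious low can set the reference and bring progression forward in a few percent of patients. Total misdating does not improve when such lows occur, and reported times and reductions may look slightly less favourable.
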